### **ABSTRACT**

**Background** Cigarette smoking is the number one preventable cause of death and morbidity in the US. A number of FDA-approved pharmacotherapies for smoking are available, however the vast majority of smokers do not respond to these medications and relapse is highly common. Risk of relapse is particularly high immediately after the initial quit attempt when nicotine withdrawal symptoms are the strongest. These findings highlight the need to continue developing novel therapies that can address smoking relapse, particularly during the initial quit attempt when relapse risk is greatest. Within the hypothalamus, the orexin (aka hypocretin) system is involved in maintaining homeostatic processes (i.e., sleep/wakefulness, food intake, etc.) through negative-feedback mechanisms. However, the orexin system also has extra-hypothalamic projections into multiple brain areas pertinent to substance use disorders (SUDs). These areas map on well to factors known to precipitate smoking relapse such as 1) disrupted sleep, 2) dysregulated stress and anxiety, 3) reaction to drug-related stimuli, and 4) drug reward. Results from both pre-clinical and recent human studies support the orexin system as a promising target to address smoking relapse. However, important human translational studies are needed carefully assessing how orexin engages each target of relapse risk.

**Proposed Study** A randomized, double-blind, parallel group, placebo-controlled design will assess an orexin receptor antagonist (suvorexant 0 vs. 20 mg) on relapse risk following overnight smoking abstinence among cigarette smokers. The ultimate goal will be to assess the impact of the orexin system on smoking relapse in a human laboratory model. Primary measures of interest will include (1) a two-component smoking relapse model (latency to smoking; reward magnitude) in which participants will have the opportunity to smoke their own cigarettes, (2) self-reported nicotine craving and withdrawal, (3) sleep metrics using self-report and actigraphy, and (4) self-reported changes in stress, anxiety, and stress reactivity using a modified cold-pressor task with a social component demonstrated to increase stress response. The current proposal seeks to obtain critical pilot data to support a future NIH grant application. To that end, the present study will demonstrate our ability to evaluate laboratory-based measures of smoking relapse risk and objective measures of sleep obtained using sleep-watch actigraphy.

### **PRIMARY HYPOTHESES AND SPECIFIC AIMS**

**Specific Aim 1:** Assess the impact of suvorexant on established measures of smoking relapse risk (craving, withdrawal, stress reactivity, latency to self-administration).

**Hypothesis 1:** Participants receiving suvorexant (vs. placebo) will demonstrate lower craving, stress reactivity, and longer latency to self-administration of cigarettes in a human laboratory experiment.

**Specific Aim 2:** Validate the somnolent effect of suvorexant on sleep metrics in a sample of individuals with tobacco use disorder.

**Hypothesis 2:** Participants receiving suvorexant (vs. placebo) will demonstrate superior sleep metrics, including higher perceived sleep quality, longer duration of sleep, lower restless sleep).

**Exploratory Aim:** Examine the potential moderating effect of suvorexant on the relationship between sleep metrics and established measures of smoking relapse (noted in Aim 1).

**Exploratory Hypothesis** The relationship between superior sleep metrics (quality, duration, restlessness) and measures of smoking relapse risk (lower craving, withdrawal, stress reactivity, and latency) will be magnified in participants receiving suvorexant (vs. placebo).

### **1. BACKGROUND AND RATIONALE**

**Public Health Impact of Smoking and Treatment Challenges** Smoking is the leading cause of death and morbidity in the U.S., responsible for nearly half a million deaths annually. FDA-approved pharmacotherapies for smoking cessation (i.e., nicotine replacement therapy, bupropion, varenicline) significantly increase the likelihood of smoking abstinence, but relapse continues to be a significant challenge. Among the millions of smokers that attempt to quit each year, most relapse within a few days of attempt. This finding is

unfortunate as remaining abstinent during the initial two weeks of the quit attempt is a robust and reliable predictor of longer-term abstinence, even when abstinence is promoted with pharmacotherapy or intensive behavioral intervention. These results highlight the importance of identifying interventions that can address relapse risk early in the quit attempt.

**Potential Targets to Address Early Smoking Relapse** Withdrawal from cigarette smoking is associated with a number of dysphoric symptoms that can precipitate smoking relapse. Below, we describe a number of key risk factors that have the potential to be addressed by targeting the orexin system.

**Dysregulated Sleep** Smokers have poorer sleep compared to non-smokers across virtually every measure of sleep quality (i.e., latency to sleep, quality of sleep, duration of sleep, time spent in deep sleep, rates of insomnia, daytime sleepiness, etc.) in studies using polysomnography as well as self-report. Smoking cessation can exacerbate poor sleep and insomnia is a clinically verified symptom of nicotine withdrawal reported by up to 42% of abstinent smokers. Studies using polysomnography and sleep diaries report reduced sleep quality shortly after smoking cessation, which normalizes 3 to 12 months later. A recent review assessed 10 studies that explicitly examined sleep metrics in relation to smoking cessation outcomes. Of 10 studies, 8 noted that sleep metrics measured before and/or during cessation predicted smoking relapse. Only one study assessed a sleep intervention (cognitive-behavioral therapy for insomnia) and observed better reported sleep quality and greater latency to smoking relapse. Interestingly, although current of FDA-approved pharmacotherapies for smoking (i.e., NRT, bupropion, varenicline) can alleviate nicotine withdrawal and craving, they all have side effects that negatively affect sleep quality (e.g., vivid dreams, insomnia, etc.). Taken together, these findings mark sleep as an important clinical target that can be impacted through clinical interventions that subsequently improve smoking outcomes.

**Stress and Anxiety** Stress and anxiety contribute to all phases of in the development of SUDs and are intimately connected with cigarette smoking. Exposure to stressors in a human laboratory setting increases craving to smoke. Smoking rates are significantly higher among populations with stress and anxiety disorders compared to the general population, and stress relief and relaxation are commonly cited as reasons for smoking. Smoking dose-dependently activates the HPA-axis, and smoking cessation results in HPA-axis hypoactivity, which is associated with more severe withdrawal and craving as well as predictive increased risk of smoking relapse.

**The Orexin System** The orexins are a class of recently discovered amino acid peptides concentrated in the hypothalamus with projections widely distributed throughout the brain including the mesolimbic reward pathway. The orexin system is neuromodulatory, increasing neural action potentials via the regulation of glutamate and GABA. A primary role appears to be in energy homeostasis, which affects systems associated with sleep, stress/anxiety, arousal, vigilance, and reward modulation. In regards to nicotine, blocking orexin transmission reduces nicotine self-administration and seeking in rats. In humans, a recent study observed that decreased orexin levels during the initial 24 hours of abstinence independently predicted time to smoking relapse. Suvorexant is an FDA-approved, schedule IV compound indicated for the treatment of insomnia. Suvorexant is an antagonist for the two currently identified orexin receptors, OX1R/OX2R, and the only compound available in the US with specificity for the orexin receptor system. We recently completed a clinical trial assessing the effects of two weeks of suvorexant on inhibitory control, drug-cue reactivity, anxiety/stress, and sleep among non-treatment seeking individuals with cocaine use disorder. This study was the first human laboratory-based experiment to examine the orexin system in human psychostimulant users, and the current proposal represents a natural extension of that study to cigarette smoking.

## METHODS

**Study Design** To accomplish the project aims, we will utilize a randomized, double-blind, parallel group, placebo-controlled design, whereby consenting participants will be block-randomized to receive suvorexant 0 mg or 20 mg. Randomization will be stratified on tobacco use disorder severity (lower vs. higher defined by Fagerström Test for Nicotine Dependence (FTND) scores < 5 vs. ≥ 5, respectively). **Table 1** (below) provides an outline of study-related procedures and assessments.

**Table 1. Outline of procedures and assessments**

	BL	Day 1	Day 8
Baseline Screening Physical Exam, Medical History, Labs, ECG, Urine Pregnancy Test, SCID, ASI, KMSK, TLFB	X		
Smoking Related Measures FTND QSU, MNWQ, Self-Report, Breath CO	X X	X	X
Stress/Anxiety Related Measures HAM-A, PSS, DASS-21, VAS	X	X	X
Sleep Related Measures PROMIS Sleep Disturbance Short Form, Epworth, PSQI Actigraphy Sleep Monitoring (Garmin Vivosmart® 3)	X	X	X
Receive 7 days of suvorexant (0 or 20 mg)		X	
Relapse Risk Assessment Stress Reactivity Assessment (HR, BP, salivary cortisol, VAS) Dual-Component Smoking Relapse Assessment		X X	X X

**SCID** - Structured Clinical Interview for DSM-5, **ASI** - Addiction Severity Index; **KMSK** - Kreek-McHugh-Schluger-Kellogg scale; **TLFB** - Timeline Followback; **FTND** – Fagerstrom Test for Nicotine Dependence; **QSU** – Questionnaire on Smoking Urges-brief; **MNWQ** – Minnesota Nicotine Withdrawal Questionnaire; **CO** – Carbon Monoxide; **HAM-A** – Hamilton Anxiety Rating Scale; **PSS** – Perceived Stress Scale; **DASS-21** – Depression Anxiety Stress Scales; **VAS** – Visual Analog Scale; **PSQI** – Pittsburgh Sleep Quality Index; **HR** – Heart Rate; **BP** – Blood Pressure

**Participant Recruitment and Setting (N = 20, n = 10/group)** will consist of otherwise healthy, cigarette smokers that report smoking at least 10 cigarettes/day, are between 18 and 65 years old and fluent in English, without greater than mild substance use disorder on drugs other than nicotine. Because suvorexant is a sedative-hypnotic contraindicated with alcohol use, participants will be excluded if they: meet DSM-5 criteria for an alcohol use disorder; report recent problem drinking (5/4 drinks for males/females in < 2.5 hours or > 10 alcoholic drinks per week); report being unwilling to stop using alcohol in the evening for the two weeks of the study; are pregnant, nursing, or planning on becoming pregnant during the course of the study; or if they have any other illness, condition, or use of medications which in the opinion of the PI and/or admitting physician would preclude safe and/or successful completion of the study. Recruitment strategies will include local advertising in print media, public service announcements on radio, and referrals to Center for Neurobehavioral Research on Addiction (CNRA) in the Houston metropolitan area. We will also recruit from the Department of Psychiatry Recruitment Registry: HSC-MS-23-0768.

**Research Team PI: [name].** [name] is an Assistant Professor in the Department of Psychiatry & Behavioral Sciences, with a primary research program involving novel applications of biostatistics and data science to health outcomes. However, his recent endeavors have expanded to first-hand research in substance use disorders and psychopharmacology, resulting in two pertinent first-author publications investigating (1) the effects of suvorexant on relapse-related factors in cocaine use disorder and (2) the strongest predictors of the first smoking lapse during a quit attempt. The present study will be supported by the infrastructure and research team at the CNRA, including **[name].**, a frequent collaborator of the PI that will assist in the implementation of the current experimental design, and mentorship from **[name].**, with expertise in psychopharmacology and the neurological bases for addiction.

**Study Medication & Medication Compliance** Participants will be randomized to receive either suvorexant 0 or 20 mg for 7 days. 20 mg is currently the highest FDA-approved dose. The bioavailability of suvorexant is > 80% and it is highly protein-bound, with a half-life of approximately 12 hours and plasma steady-state is reached within three days. Because suvorexant is a hypnotic with a moderate half-life, participants will be informed to take the medication at 10:00 PM. Compliance will be assessed using both Medication Event Monitoring Systems (MEMS) pill bottles that record the time/frequency of bottle openings as well as riboflavin.

### **Measures**

**Baseline Screening** As part of the CNRA general evaluation protocol (HSC-MS-05-0322), to determine eligibility, participants will receive a comprehensive medical and psychiatric evaluation including: a medical-history questionnaire, physical examination, laboratory chemistries (e.g., blood chemistry screen, complete blood count, urinalysis and urine pregnancy test), and ECG. Clinicians will conduct the **SCID**, the **ASI**, the **KMSK** assessment of lifetime substance use interview, and **TLFB**.

**Smoking-Related Measures** Nicotine dependence will be assessed using the **FTND**. Self-report will be used to collect self-reported number of cigarettes used in the past 7 days. Nicotine craving will be assessed using a brief, 10-item version of the **Questionnaire of Smoking Urges (QSU-brief)**. Nicotine withdrawal will be assessed using the 8-item **MNWQ**. **Breath CO** will be used to measure severity of smoking and overnight smoking abstinence.

**Sleep-Related Measures** Quality of sleep in the past week will be primarily assessed using the **PROMIS Sleep Disturbance Short Form**, a well validated and reliable subjective measure of sleep quality. Secondary measures will include the **Epworth Sleepiness Scale**, and **PSQI**. Sleep actigraphy (total hours, levels, and movement) will be measured via the Garmin Vivosmart® 3 device as validated by recent research.

**Stress and Anxiety Measures** Stress and anxiety will be assessed using standard, validated questionnaires using the **HAM-A**, **PSS**, and **DASS-21**. Additionally, a single-item **VAS** measure will be used to assess self-reported stress.

**Human Laboratory Measures** Experimental measures will be conducted on study days 1 and 8. Participants will be instructed to stop smoking by 10 pm the day before, in order to ensure they meet the breath CO criterion ( $CO \leq 4$  ppm) indicating overnight abstinence. In addition to measuring nicotine craving and withdrawal using the QSU and MNWQ, respectively, we will conduct two additional assessments.

**Stress Reactivity** Stress reactivity will be assessed using a modified version of the CPT on study days 1 and 8. The CPT involves participants submerging their dominant arm in an ice-water bath for up to 2 min. The CPT is widely used to induce stress in human laboratory studies and activates major stress systems in the body. Stress activation can be significantly increased by incorporating a social evaluative component, which will be done by having a study member present wearing a white lab coat and holding a clipboard. Participants will also be videotaped and informed that their facial expressions will be assessed. Stress levels will be assessed using both subjective and physiological measures, including HR, BP, and salivary cortisol, consistent with previous studies from our group.

**Smoking Relapse Assessment** A dual-component smoking relapse assessment will be conducted in which participants will have the opportunity to self-administer their preferred brand of cigarettes. Participants will earn \$1 for every 5 min they do not smoke for the first 50 minutes (for a total of \$10). At 50 minutes or once participants indicate they want to smoke, they will be given \$7 to either purchase their preferred brand of cigarettes (\$1 per cigarette) or keep. The two dependent variables will be latency to smoke the first cigarette and total number of cigarettes smoked.

**Study Compensation** Participants will be provided \$40 for completing the baseline screening. They will receive \$50 for attending each study visit and a \$50 bonus for completing the study/returning study equipment. Additionally, participants will receive \$5 compensation per visit for parking and/or bus fare. As noted above, participants may earn up to \$34 across visits during the smoking relapse assessment (if achieving maximum latency and zero cigarette purchase), bringing total possible compensation to \$234/participant. Upon study completion, participants may be given the opportunity to earn an additional \$20 for referring new participants to the study that successfully enroll and also complete all study procedures.

## DATA ANALYSIS PLAN

**Confounding Variables** Preliminary data analyses will inspect relationships between baseline/demographic variables, experimental group, and specified outcome variables via traditional statistical tests (e.g., chi-square, Mann-Whitney-Wilcoxon, Kruskal-Wallis, and *t*-tests). Baseline covariates that demonstrate a relationship with both assigned group and outcome variables meet criteria for being potential confounders and will be included as a covariate in any statistical models for hypothesis testing. All analyses will statistically control for the stratification variables (detailed above in the Study Design section).

**Inferential Paradigm** Following recommendations for clinical trials in the literature analyses will proceed using parallel frequentist and Bayesian statistical inference. Frequentist results yield The probability of the data (or data more extreme), given the null hypothesis, while Bayesian results yield The probability of the null hypothesis given the data and The probability of the alternative hypothesis given the data.

alternative hypothesis. If possible, Bayesian analyses will incorporate informative priors as they develop in the literature; otherwise, weakly informative priors will be incorporated as a default (e.g., for regression coefficients:  $\sim N[\mu=0, \sigma^2=100]$ ; for non-linear outcomes this prior applies to the coefficient within the link-function). Sensitivity analyses using optimistic and pessimistic, skeptical priors will evaluate prior assumptions. Assessing the convergence of Bayesian analyses on the posterior distributions via Monte-Carlo Markov chain (MCMC) will use graphical (Trace Plot, Autocorrelation Plot) and quantitative (Geweke Diagnostics, Gelman-Rubin Diagnostics, and Heidelberger-Welsh Diagnostics) evidence. Evaluation of posterior distributions will permit statements regarding the probability that effects of varying magnitudes exist, given the data. Statistical analyses will use SAS v. 9.4 and the most up-to-date stable release version of the R statistical computing environment using packages rstan and brms.

**Statistical Modeling** Analyses will primarily use generalized linear modeling (GLM) with multilevel components (GLMM) for correlated observations. Specifically, for each hypothesis, GLMM will model each outcome measure of interest as a function of group, potential confounding variables (as described above), and random effects to account for correlated observations where necessary. Continuous, count, and dichotomous outcomes will utilize normal, Poisson/negative binomial, and binomial distribution families respectively, with identity, log, and logit link functions as appropriate. Evaluation of distributional assumptions will use residual plots, formal statistical tests, and posterior predictive checking. Violations of assumptions will be addressed via transformation, robust estimation, stratification, and/or coefficient scaling where appropriate.

**Missingness & Multiple Comparisons** While the short nature of the proposed trial should reduce the prospect of missing data, for the frequentist analyses, missing data will be addressed via maximum likelihood, explicit modeling of missingness, and/or imputation. Bayesian analyses will use joint modeling of outcomes and missingness to handle missing data. Each approach is robust to ignorable missingness (i.e. MCAR and MAR). Analyses will address non-ignorable missingness using pattern-mixture modeling. Sensitivity analyses will permit evaluation of the robustness of findings to missing data assumptions. While Bayesian analyses are not influenced by traditional concerns of multiplicity, frequentist analyses will utilize false discovery rate (FDR) to control for Type I error across multiple tests for secondary outcomes where delineated.

**Exploratory Data Analyses** Where not otherwise specified, to maximize the utility of the present data, exploratory analyses will evaluate relationships between variables captured as part of the study. For example, while not represented in specific hypotheses, changes in self-reported smoking behavior as functions of other variables in the present study will be explored.

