### **Specific Analyses**

Hypothesis 1: GLMM will model each primary relapse risk outcome (craving (QSU), stress reactivity (heart rate and salivary cortisol), and latency to self-administration) as a function of the main effects and interaction between time (pre vs. post) and treatment group, including any necessary control variables (as defined above in the confounding variables section) and a random intercept for participant. Secondary measures of craving and stress reactivity will be assessed in similar fashion with Type I error correction for the frequentist analyses.

Hypothesis 2: GLMM will model each sleep metric (quality, duration, and restlessness) as a function of the main effects and interaction between time (pre vs. post) and treatment group, including control variables and a random intercept for participant. Secondary measures for sleep will be assessed in similar fashion with Type I error correction for the frequentist analyses.

Exploratory Hypothesis GLMM will model each relapse risk outcome (craving, stress reactivity, and latency to self-administration) as a function of the main effects and all higher-order interactions between time (pre vs. post), given sleep metrics (in unique models: quality, duration, and restlessness), and treatment group, including control variables and a random intercept for participant.

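### Covariates are picked by testing baseline variables against group and outcome; the screen adds no useful adjustment to the planned model and should give way to a fixed set including the Day 1 value

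*Combined protocol and SAP*

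**What the plan says.** The Confounding Variables paragraph of the Data Analysis Plan first examines how baseline and demographic variables relate to group and to outcome, "via traditional statistical tests (e.g., chi-square, Mann-Whitney-Wilcoxon, Kruskal-Wallis" and t-tests being the examples given. It then states the rule: "Baseline covariates that demonstrate a relationship with both assigned group and outcome variables meet criteria for being potential confounders". Variables that meet it "will be included as a covariate in any statistical models for hypothesis testing". There is no significance threshold and no list of candidates.

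The same paragraph ends with a separate commitment that does not depend on any test: "All analyses will statistically control for the stratification variables". For what those variables are it points back to Study Design, where "Randomization will be stratified on tobacco use disorder severity" (FTND below 5 versus 5 or more). Section E1 names three factors instead: sex, FTND and QSU-brief.

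Under Specific Analyses, each Hypothesis 1 outcome is modelled "as a function of the main effects and interaction between time (pre vs. post) and treatment group". The screened covariates come in by a cross-reference to the paragraph above, and the participant-level term is "a random intercept for participant". Hypothesis 2 uses the same form, again with control variables. No Day 8-only model is planned for either hypothesis.

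**The concern.** Allocation is randomised, so any baseline difference between arms is chance, and a test of it answers no useful question. The rule also consults the outcome. Heart rate, cortisol, craving, latency and each sleep metric could therefore be analysed with different covariates, settled only once the data are in hand. With neither a threshold nor a candidate list, two analysts following the plan could report different models.

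The best-placed covariate for a continuous outcome is likely to be its own Day 1 value, which is known in advance. The planned model uses that value as the 'pre' response, not as a covariate. So the plan spends analyst discretion on screening and leaves a predictable gain in precision unused, in a trial capped at 20 participants whose estimates are meant to support a larger one.

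**Working it through.** **Inputs from the documents.** N = 20, 10 per group; alpha = 0.05; Cohen's f = 0.66 at 80% power (Sample Size and Power Considerations); two measurement days, 1 and 8; random intercept; normal family with identity link for continuous outcomes.

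**Assumptions, not in the documents.** Day 1 to Day 8 correlation ρ of 0.3, 0.5 or 0.7; equal SD on both days; selection threshold 0.05 to 0.20; 1 to 15 candidates. Table 1 lists more than ten baseline measures.

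**1. The plan's own figure.** For two equal groups λ = f²N = 0.66² × 20 = 8.71. A noncentral F with 1 and 18 df gives power 0.797, matching the stated 80%. In SD units d = 2f = 1.32.

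**2. What a screened covariate does in the planned model.** Write Dᵢ = Yᵢ(Day 8) − Yᵢ(Day 1). The random intercept and any time-fixed covariate entered as a main effect cancel from Dᵢ. With complete data and an identity link, the group-by-time estimate is the difference between arms in mean D, whatever covariates are present.
- Complete data: models fitted with and without a time-fixed covariate gave a shift of 0.0000 in all 55 simulated data sets. The standard error was unchanged unless the random-intercept variance fell to zero (lowest ratio 0.953).
- 2 of 20 Day 8 values missing: the estimate moved by a median of 0.02 to 0.05 SD and at most 0.13 SD, so it then depends on which covariates passed.

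**3. Planned contrast against Day 1 adjustment, d = 1.32, 10 per arm, two-sided 0.05.** The change score has SD √(2(1−ρ)), tested on 18 df. Adjusting Day 8 for Day 1 leaves residual SD √(1−ρ²), on 17 df, averaged over chance imbalance in the Day 1 value.

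| ρ | SD of change | Power, planned contrast | Residual SD, adjusted | Power, Day 1 adjusted |
|---|---|---|---|---|
| 0.3 | 1.183 | about 65% | 0.954 | about 81% |
| 0.5 | 1.000 | about 80% | 0.866 | about 88% |
| 0.7 | 0.775 | about 95% | 0.714 | about 96% |

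At ρ = 0.5, adding strata balanced by arm brings the 88% to about 87% (one factor) or 85% (three).

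**4. If the screen were carried into a Day 8 model (ρ = 0.5, d = 1.32).**

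| Candidates | Threshold | Power under rule | Power unadjusted | Power, Day 1 fixed | Bias under rule (SD) |
|---|---|---|---|---|---|
| 1 | range | 0.795–0.804 | 0.798 | 0.877 | −0.011 to −0.021 |
| 10 | 0.05 | 0.75 | 0.79 | 0.87 | −0.05 to −0.07 |
| 10 | 0.20 | 0.66–0.71 | 0.79 | 0.87 | −0.12 to −0.15 |

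The bias arises because, when there is a true effect, a covariate imbalanced in the same direction as that effect passes both tests more often (4.6% against 0.4% at threshold 0.05 with one candidate). With no true effect there is no bias, and Type I error is 0.026 to 0.048, so it is not inflated.

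**The case against.** The strongest reply is that the screen does almost nothing in the analysis actually planned. That is correct for the group-by-time term under the conditions in step 2. A reader might infer from step 4 that the planned analysis loses power or is biased. The documents do not support that, because no Day 8-only model is planned and those figures apply only if the rule is carried over into one. Nor can the rule be called inert without conditions: the plan allows for missing data and for log and logit links, where the cancellation is not exact.

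A reader might also infer that the strata are adjusted for only when imbalanced. The plan says the opposite.

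It is tempting to cite the chance that at least one of 10 or 15 independent variables differs by arm at p < 0.05: 1 − 0.95¹⁰ = 40%, 1 − 0.95¹⁵ = 54%. These count imbalance with group only, whereas the rule also requires a relationship with outcome, and the listed scales overlap. With 10 candidates at threshold 0.05, simulated selection rates were about 5% to 12%.

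Two further replies have some force. The power gain in step 3 comes from changing the model form and is not damage done by screening. The gain also shrinks if strata terms are added without balance by arm: at ρ = 0.5, power was 85% with one such factor and 80% with three, no better than the planned contrast. Stratified randomisation is meant to secure that balance, but the result does depend on it.

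**Conclusion.** The point holds in limited form. The rule is data-driven, lacks a threshold and a candidate list, and gives no useful adjustment to the planned group-by-time estimate. With a few missing Day 8 values it makes that estimate depend slightly on which tests were passed (up to about 0.13 SD in the simulated cases). A fixed Day 1 adjustment would add about 15 points of power at ρ = 0.3, 8 at 0.5 and 1 at 0.7 before strata terms, which cost roughly 1 to 3 points at ρ = 0.5 when balanced by arm and more when not. These sizes rest on the assumed correlations, since the documents give none, and on continuous outcomes with an identity link. Transferring the screen to a Day 8 model would be harmful with about ten candidates and trivial with one. Severity is modest: the plan describes the work as exploratory, and Type I error is not at risk.

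**What to change.** Delete the screening rule and show baseline variables by arm descriptively, without tests. For continuous Hypothesis 1 and 2 outcomes, make the Day 8 value the response, with treatment group, the Day 1 value of the same outcome and the stratification factor(s) actually used as one fixed set of terms. Reconcile Study Design (FTND only) with section E1 (sex, FTND and QSU-brief) so that the strata are unambiguous. Do not carry the screen into the Day 8 model.

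This needs only a change of wording and uses measurements already planned. The downside is a few degrees of freedom and a change in the form of the primary model, so it should be settled before unblinding.
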